
Objectives:

Primary: The successful administration of simulated naloxone without training. A successful administration will be defined as administration of the simulated naloxone to the mannequin head or simulated flesh pad within 7 minutes and without any critical errors (defined below).

Secondary:

-Total time required to successfully administer the simulated naloxone without training.

- Comparison of successful administration with standard and simplified instructions
- Comparison of total time required for successful administration with standard and simplified instructions
- Likert-item assessment of the usability of the simulated naloxone product
- Likert-item assessment of usability of the naloxone administration instructions

Design: Single site, open-label, randomized usability assessment of intramuscular, intranasal, and nasal spray administration of simulated naloxone using standard (package-insert) or simplified (developed by study team) instructions. A convenience sample of participants will consent to volunteer in the study at a public venue. Participants will provide verbal consent and will be randomly assigned a simulated naloxone kit containing either intramuscular standard, intramuscular simplified, intranasal standard, intranasal simplified, nasal spray standard, or nasal spray simplified administration materials. The participant will enter a use scenario station where they will be asked to assemble and administer the simulated naloxone kit to a mannequin (intranasal and nasal spray) or simulated flesh pad (intramuscular). The participant will be instructed to start and will be timed until the simulated naloxone has been successfully administered or 7 minutes has elapsed. The participant will be observed by one trained investigator who will assess for successful administration of the simulated naloxone and critical errors. The environment will contain distracters to mimic a community based setting. Once the participant has successfully administered the simulated naloxone or 7 minutes has elapsed the timer will be stopped. Successful administration of simulated naloxone will be defined as administration of the agent without any critical errors occurring (defined below). Data collected will include demographics (defined below), successful administration of simulated naloxone, product assessment information, instruction assessment information, and time to successful administration of simulated naloxone.

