Eligibility: healthy adults (18 years of age and older) at a public venue will be asked to participate in the study. Participants will be excluded if they are severely visually or hearing impaired (defined as: legally deaf, legally blind, unable to read print size provided on instructional handout, or unable to hear instructions from a research staff member), have previous naloxone administration training, are not English proficient, state that they may be pregnant, or they have previously participated in the trial.

Statistical Methods: All data will be analyzed using IBM SPSS Statistics software. Demographics data will be analyzed using descriptive statistics for continuous measures and percentages for categorical measures. The successful administration of naloxone will be compared between groups using the Chi-square test and a significant difference will be defined as a p-value of less than 0.05 for the result. The time to administration between groups will be assessed using a one-way ANOVA and a significant difference will be defined as a p-value of less than 0.05 for the result. The Likert-item data will be reported as percentage of response level and analyzed using a one-way ANOVA with a significant difference defined as a p-value of less than 0.05 for comparison between administration methods and instruction methods.

Data Analysis/Interpretation: As stated above data will be collected to assess both the successful administration of and time to administration of naloxone. The rate of successful administration will be

reported as a percentage for each of the three groups and analyzed using the Chi-square test. Successful administration is defined as administration of the simulated naloxone within 7 minutes without committing any critical errors. Critical errors are as follows:

[figure not shown]
- Intranasal (atomizer): failure to remove both yellow caps from bristoject, failure to remove cap from simulated naloxone, failure to attach atomizer, failure to attach simulated naloxone, drug leak prior to administration, administration in only one nostril, and failure to administer within 7 minutes.
- Intramuscular: failure to attach the needle to the syringe, failure to remove cap from simulated naloxone, failure to draw up >90% (0.9 mL) of the simulated naloxone, failure to puncture simulated flesh pad with needle, failure to push entire volume of fluid in the syringe into the simulated flesh pad, and failure to administer within 7 minutes.

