- Intranasal (spray): failure to place the tip of the device into one nostril, failure to depress the device and release the simulated naloxone, failure to administer within 7 minutes.

Time to successful administration will be reported using descriptive statistics (mean time to administration) and analyzed using a one-way ANOVA. Times for participants who commit a critical error or who do not administer the simulated naloxone within 7 minutes will not be included in the analysis. The Likert-item data will be reported as a median with an inter-quartile range and analyzed using a one-way ANOVA.

A route of administration will be considered to be more user-friendly if it demonstrates a statistically significantly higher rate of successful administration compared to another route of administration. Additionally, a route or instruction type will be considered user preferred if the Likert-item data demonstrates a significantly better score on usability.

Study Procedures: No study procedures will be performed on study participants.

Diagram of Study Design:

Investigators observe the administration and record if the administration is successful, the time to administration, and the critical error that occurred if applicable. Survey data is

Works Cited

1. Volkow ND. America's Addiction to Opioids: Heroin and Prescription Drug Abuse. <https://www.drugabuse.gov/about-nida/legislative-activities/testimony-to-congress/2016/americas-addiction-to-opioids-heroin-prescription-drug-abuse>. Published May 14, 2014. Accessed June 24, 2016.

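### Instruction comparisons of success and time get one-factor tests that ignore route, although six route-by-instruction kits are randomised; the consequence is mainly for time

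*Combined protocol and SAP*

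**What the plan says.** The Design section assigns each participant at random to one of six kits: "intramuscular standard, intramuscular simplified, intranasal standard, intranasal simplified, nasal spray standard, or nasal spray simplified administration materials". The secondary objectives include "Comparison of successful administration with standard and simplified instructions" and "Comparison of total time required for successful administration with standard and simplified instructions".

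Statistical Methods gives one sentence for each outcome: "The successful administration of naloxone will be compared between groups using the Chi-square test" and "The time to administration between groups will be assessed using a one-way ANOVA". Neither says which factor forms the groups. Only the Likert sentence names both factors: "for comparison between administration methods and instruction methods".

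Under Data Analysis/Interpretation, success is to be "reported as a percentage for each of the three groups and analyzed using the Chi-square test". The critical errors that follow are listed by route, and the rule for calling a route more user-friendly compares one route with another, so these groups are the three routes. The same section restricts the time analysis: "Times for participants who commit a critical error or who do not administer the simulated naloxone within 7 minutes will not be included".

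The text commits to no six-kit table, no success rate by route under the package insert, and no instruction comparison stratified by or adjusted for route. The design diagram is not available in the text, so this point concerns the written plan only.

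**The concern.** Two things are lost when a three-by-two design is analysed one factor at a time.

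**Success.** Route percentages pooled over instruction type cannot show how each route does with the package insert. The Background motivates the study by over-the-counter purchase with less chance of training, so that rate is of direct interest, although it is not the stated primary objective. A gain confined to one kit would appear as a general instruction effect.

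**Time.** Randomisation balances route between instruction groups among all participants, but not among those who succeed. If simplified instructions rescue more users of a slow kit, the simplified group holds more slow-kit times and can look slower, or lose a real gain, only because of its route mix. Differences between routes also stay in the error term and cost power.

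**Working it through.** **Inputs.** The six kits, the tests and the restriction to successes come from the plan. It states no sample size, allocation ratio, success rates or times. Everything numerical below is therefore assumed: equal arms of 50, two-sided 5%, time SD 50 s within a kit. Success patterns are standard/simplified, in %, with kits ordered slowest to fastest:

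- strong route differences: 30/45, 45/60, 95/97
- moderate: 50/65, 60/75, 75/90
- one kit only: 40/80, 60/60, 60/60

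**Step 1: what three percentages hide.** Kit rates of 40/80, 60/60, 80/80 average to 60/60/80 by route. Rates of 60/60, 60/60, 80/80 give the same 60/60/80. Success with the package insert in the first route is 40% in one case and 60% in the other.

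**Step 2: shift in mean time with no true instruction effect.** With success rate s and mean time m in each kit, the expected mean among successes in an instruction group is about Σ(s·m)/Σs.

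| Pattern | Route means (s) | Standard | Simplified | Shift |
|---|---|---|---|---|
| Strong | 150/120/40 | 13,700/170 = 80.6 | 17,830/202 = 88.3 | +7.7 s |
| One kit | 150/120/40 | 15,600/160 = 97.5 | 21,600/200 = 108.0 | +10.5 s |
| Moderate | 150/120/40 | 17,700/185 = 95.7 | 22,350/230 = 97.2 | +1.5 s |
| One kit | 120/100/80 | 15,600/160 = 97.5 | 20,400/200 = 102.0 | +4.5 s |
| Moderate | 120/100/80 | 18,000/185 = 97.3 | 22,500/230 = 97.8 | +0.5 s |

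Simulation agrees (up to 10.6 s in the one-kit case). With equal route means the shift is zero. The direction is not fixed: with the one-kit effect in the fast kit (60/60, 60/60, 40/80; means 150/120/40 s) the means are 17,800/160 = 111.25 and 19,400/200 = 97.0, so simplified looks 14.25 s faster.

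**Step 3: power for a true 15 s gain, moderate pattern, means 150/120/40 s.**

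- *Route + instruction model.* Expected successes per kit are 25/32.5, 30/37.5 and 37.5/45. The information is Σ n₀n₁/(n₀+n₁) = 14.13 + 16.67 + 20.45 = 51.25. SE = 50/√51.25 = 6.98 s, and power is about Φ(15/6.98 − 1.96) = Φ(0.19), or 57%.
- *Pooled ANOVA on instructions.* The spread of route means adds about 2,240 s² to the within-kit variance of 2,500 s², so SD ≈ √4,740 = 68.9 s. SE = 68.9 × √(1/92.5 + 1/115) = 9.62 s. The apparent gain is 15 − 1.5 = 13.5 s, against a critical difference of 1.96 × 9.62 = 18.9 s. Simulated power is 24 to 25%.

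Here most of the loss comes from route spread left in the error term, and little from bias.

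**Step 4: simulated power in other cases, pooled v route + instruction.**

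- Strong, 150/120/40 s: 6 to 7% v 52%
- Moderate, 120/100/80 s: 50 to 52% v 57 to 59%
- One kit, 120/100/80 s: 25% v 50%

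**Step 5: false-positive rate of the pooled time test with no true effect.** At 150/120/40 s it is about 7% (strong), 13% (one kit) and 1.9% (moderate). At 120/100/80 s it is 4.6% (moderate). The two-factor model gave 4.8% in the strong case and 5% in the one-kit case.

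**Step 6: instruction effect on success, pooled chi-square v Cochran-Mantel-Haenszel (CMH) over routes.** Power is 47% v 60% (strong), 82% v 83% (moderate), and 77% v 77% in a weak case (50/65, 55/70, 60/75). With a continuity correction CMH falls below the pooled test: 79% v 82% in the moderate case and 73% v 77% in the weak case.

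**The case against.** The best defence is that the main analysis is clear and sound. Context identifies the three groups as the routes, the decision rule compares routes, and under balanced allocation a route comparison averaged over both instruction sheets is valid. All of that stands. No objective asks for an interaction or for route rates within one instruction type, and the pooled instruction comparison of success validly estimates an average effect. That stands too, so the six-kit table is an added description and does not correct an error.

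The time problem also depends on a reading. It arises only if the ANOVA compares instruction types pooled over route. A six-arm ANOVA would not have it, although that would not isolate an instruction effect either. It further needs kits that differ in speed; bias also needs a success effect that shifts the route mix. In milder cases the bias is 0.5 to 1.5 s and the false-positive rate is not raised. This limits the size of the point but does not remove it: the secondary objective asks for a standard-versus-simplified comparison of time, and the only method offered has one factor.

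A reader might infer more than the documents support:

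- *That the primary comparison misses effects.* In the one-kit pattern all three route averages are 60%, so a three-route test that rejects 4% of the time is behaving correctly under a true null.
- *That an interaction test is needed.* It rejects 88% of the time for 40/80 in one kit, but 63% for 45/75, 31% for 50/70, and only about 5 to 10% in the strong, moderate and weak patterns.
- *That ignoring route seriously weakens the success comparison.* The gain from adjustment is 0 to 1 points unless routes differ strongly.

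**Conclusion.** The point holds as a gap in the secondary analyses. The standard-versus-simplified comparisons are given one-factor tests that do not account for the other randomised factor, and success is tabulated by route alone.

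The consequence is greatest for time. A pooled instruction ANOVA restricted to successes is biased by about 0.5 to 10.6 s in the five tabulated scenarios, and it loses between a few and about 45 points of power for a true 15 s gain. All of this rests on assumed success rates, route means, SD and arm size. There is no bias and no gain if route times are equal. For success the loss is mainly descriptive, and adjustment matters only when routes differ strongly. Nothing here undermines the primary route comparison.

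**What to change.** - State the factor for each test: route for the primary comparison of success, instruction type for the secondary comparisons.
- Replace the one-way ANOVA of time on instructions with a model containing route and instruction.
- Compare success between instruction types stratified by or adjusted for route (CMH without continuity correction, or a two-factor logistic model), noting that the gain is small unless routes differ strongly. Cells near 100% need an exact or penalised fit.
- Report all six kit success rates with confidence intervals as descriptive estimates, including the route rates under the package insert, without a separate test.
- Treat a route-by-instruction interaction test as optional and exploratory. With no true effects, route and instruction tests at 5% give at least one false positive 10.0% of the time; adding the interaction test raises this to 14.8%.

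**Cost.** Analysis wording only, with no new participants or data. Kit intervals will be wide: a 60% rate has a 95% Wilson interval of about 46 to 72% at 50 per kit and 42 to 75% at 30. The time model removes the shift in route mix but not the selection of successful participants within a kit, so the time result still describes successes only.

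### Incomplete delivery is a critical error for the intramuscular route but is not on the printed atomizer list, so the route comparison rests on unequal success rules with an unknown net effect

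*Combined protocol and SAP*

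**What the plan says.** The primary objective defines success in two parts: "administration of the simulated naloxone to the mannequin head or simulated flesh pad within 7 minutes", and no critical error. Data Analysis/Interpretation then lists the critical errors for each route.

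- Intramuscular: two items concern volume, "failure to draw up >90% (0.9 mL) of the simulated naloxone" and "failure to push entire volume of fluid in the syringe into the simulated flesh pad".
- Atomizer: after the cap and assembly items, the printed list ends with "drug leak prior to administration, administration in only one nostril, and failure to administer within 7 minutes". No item concerns the volume expelled.
- Spray: the delivery item is "failure to depress the device and release the simulated naloxone". It does not say whether release means full delivery, and only one nostril is asked for.

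Under Design, the study is open-label and each participant is watched by one trained investigator "who will assess for successful administration of the simulated naloxone and critical errors". The text beside the study diagram has investigators record a critical error in the singular.

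Success is compared between groups by Chi-square at 0.05. The decision rule reads: "A route of administration will be considered to be more user-friendly if it demonstrates a statistically significantly higher rate of successful administration". For the time analysis, "Times for participants who commit a critical error" are left out, as are times of those who run past the limit.

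**The concern.** Different devices need different assembly items. Whether the fluid was actually delivered, however, is a question common to both syringe-based routes, and the plan writes it down as critical for only one of them. A participant who stops half-way through the push fails on the intramuscular route. A participant who sprays half the fluid, some into each nostril, commits no listed error on the atomizer.

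These lists define the primary endpoint, and a significant route difference earns the label of greater user-friendliness. Unequal rules can create such a difference where none exists, or hide a real one. The same rules decide which times enter the ANOVA: an incomplete injection is removed, while an incomplete atomizer spray can stay in. If under-delivery is rare, both effects are negligible.

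**Working it through.** **Side-by-side reading of the lists**

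| Event | Intramuscular | Atomizer (printed list) |
|---|---|---|
| Syringe not emptied | Fails | No listed error |
| Small loss before delivery | Draw-up loss under 10% passes | Any leak fails |
| Full volume, one nostril | No counterpart | Fails |

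The draw-up item gives 0.9 mL as 90%, so the full volume is 0.9/0.90 = 1.0 mL and the tolerated loss is just under 0.1 mL. The first row, taken alone, raises atomizer success relative to intramuscular. The second and third lower it. Hence:

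net shift = atomizer users passed despite under-delivery − atomizer users failed only for a small leak or only for using one nostril.

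The documents give none of these rates, so neither the sign nor the size of the net shift can be derived.

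**Illustration of what a shift would do**

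The documents give no sample size, success rate or under-delivery rate, so there is no figure of the plan to reproduce. Every input here is assumed except the 0.05 level. With n per route, intramuscular success p and atomizer success p + s, the Pearson statistic without continuity correction is

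X² = (difference in observed proportions)² / [2 × p̄ × (1 − p̄) / n], with p̄ the pooled proportion.

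The chance of significance is the sum of the product of the two binomial probabilities over all outcomes with X² > 3.84. For p = 60%:

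| Net shift s (points) | −10 | −5 | −2 | 0 | +2 | +5 | +10 |
|---|---|---|---|---|---|---|---|
| n = 50 | 18.4% | 8.5% | 5.8% | 5.2% | 5.7% | 8.2% | 18.0% |
| n = 100 | 31.0% | 11.6% | 6.2% | 5.1% | 6.0% | 11.3% | 31.6% |
| n = 150 | 43.1% | 14.9% | 6.7% | 5.2% | 6.6% | 14.5% | 44.0% |

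At n = 100 with p from 40% to 80%, and either sign, the ranges are 6.0-6.7% at 2 points, 11.3-15.6% at 5 and 30.8-51.8% at 10.

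*Masking.* If intramuscular were truly 15 points better (60% v 45%, n = 100), power is 58.6% at no shift and 47.3%, 31.0% and 11.6% at +2, +5 and +10 points.

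*How much under-delivery a shift needs.* Let f be the share of atomizer users with no listed error who under-deliver, with 60% succeeding in full and no offset from the leak and nostril rules. Then s = 60 × f/(1 − f):

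- f = 3%: 60 × 0.03/0.97 = 1.9 points
- f = 8%: 60 × 0.08/0.92 = 5.2 points
- f = 14%: 60 × 0.14/0.86 = 9.8 points

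*Offsets.* If 5 points were passed for under-delivery and 2 points failed under the two stricter atomizer rules, the net shift is 3 points and the chance is 7.3%. If the two cancel, it is 5.1%.

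*Times.* With u points of under-deliverers and no offset, their share of analysed atomizer times is u/(60 + u): 2/62 = 3.2%, 5/65 = 7.7%, 10/70 = 14.3%. An assumed 30 s gap, in either direction, moves the atomizer mean by 1.0, 2.3 or 4.3 s, against a limit of 7 minutes (420 s).

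**The case against.** The best defence has four parts.

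1. **The error list is not the whole success rule.** Administration to the target is a separate condition, and the observer judges it separately from critical errors. A reader might infer that the plan obliges the observer to pass a partial spray. It does not: having no listed error is necessary for success, not sufficient. What remains is that no amount is stated, so an unblinded observer has no written standard for a partial spray, whereas the intramuscular standard is explicit.

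2. **The leak and two-nostril rules offset the gap.** A reader might infer that the lists favour the atomizer, more so because the Background reports that the sponsor's 2016 study found higher success with the intranasal routes. The documents do not support that. Two atomizer rules are stricter than their intramuscular counterparts, and nothing shows which effect is larger. This part of the defence stands in full and limits the point to one of unequal rules. Each of these errors may well be a genuine failure; the issue is only that they are treated differently across routes.

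3. **Part of the plan may be out of sight.** A figure just before the lists is not shown and might hold more detail. This also stands, so the point is confined to the printed lists.

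4. **Device-specific lists, fixed in advance, are normal.** That is true of assembly steps. It does not explain why emptying the syringe is critical on one syringe-based route and unlisted on the other.

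**Conclusion.** The point holds for the route comparison: the printed lists apply different completeness-of-delivery rules to intramuscular and atomizer users, and the plan neither explains nor tests the difference. The net shift has unknown sign and unknown size, and may be small.

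The percentages above are illustrations, not estimates of error in this trial. At the 60% and 100-per-route assumptions, a net shift of 2 points barely matters and one of 10 points matters a great deal. The latter would need about 14% of otherwise error-free atomizer users to under-deliver with no offset at all. The effect on mean times looks minor under the assumed gap.

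Comparisons of standard with simplified instructions within a route use one list for both arms and are unaffected. The matter is worth settling before launch because it touches the primary endpoint, and the data needed to examine it afterwards may not otherwise be collected.

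**What to change.** Before data collection:

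1. **Reconcile the lists.** Apply the same completeness-of-delivery standard to the intramuscular and atomizer routes by adding an atomizer item for failure to expel the fluid, scored by the existing observer. The tolerance is for the sponsor to set. State also whether release, in the spray list, means full delivery.
2. **Record every critical error.** Change the recording beside the study diagram from a single critical error to all that occurred. Without this, nobody can tell who failed only on a delivery item, and step 3 cannot be done.
3. **Add a sensitivity analysis.** Report the route comparison with the full lists, and again without the items that differ on delivery: intramuscular draw-up and full push; atomizer expulsion, leak and one-nostril use. Still require that some product reaches the target, so that an empty syringe does not pass. If the two analyses disagree, say that the user-friendliness label depends on how delivery is scored.

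The cost is one form item, multiple-error recording, a clarifying sentence for the spray and one extra analysis, with no added participants. Atomizer success may come out slightly lower. The documents do not say whether residual fluid can be judged by eye, so the sponsor should check this before launch. If it cannot, the sensitivity analysis carries more of the weight.

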Protocol: A usability assessment of intramuscular, atomized intranasal, and nasal spray administration of naloxone by untrained community members

Primary Investigator: [name]

Background: Opioid abuse and addiction is a growing epidemic both in the United States and globally. It impacts the health, social welfare, and economic stability of those directly affected and society as a whole. According to the National Institute on Drug Abuse there are approximately 2.1 million people in the United States with substance use disorders related to prescription opioid medications and another 467,000 addicted to heroin. Data from the Center for Disease Control National Vital Statistics System demonstrated that the number of drug poisonings involving opioid analgesics tripled from 2000 to 2014, and in 2010 opioid pain relievers were responsible for 82.8% of all unintentional deaths in the United States.¹ In an attempt to combat this epidemic many states have implemented community-based opioid overdose prevention programs aimed at increasing resources to combat addiction and distributing naloxone to community members. These programs increase knowledge of overdose prevention and the factors that increase a person's risk for overdose. Evaluations of these programs have also demonstrated that nonmedical bystanders are able to administer naloxone effectively after completing training.² Naloxone can be administered intravenously, intramuscularly, or via inhalation. Opioid overdose prevention programs are typically initiated by local and state governments, which allows for interprogram variability regarding the route of naloxone administration used by community members. Pre-hospital data has demonstrated that intranasal naloxone is a safe and effective alternative to intravenous naloxone.³ A usability assessment comparing a naloxone auto-injector (Evzio®) to the use of a nasal atomizer suggested that the route of administration did impact the rate of successful naloxone administration by nonmedical community members.⁴ Opioid overdose prevention programs typically utilize intranasal atomizers, nasal inhalers, or intramuscular administration routes. In 2016 we conducted a usability assessment of naloxone administered by community members who received training on how to use the naloxone device they were assigned. Our data supported that intranasal administration with an atomizer or spray resulted in a higher administration success rate when compared to intramuscular injection. Recently, New York, along with many other states, passed legislation allowing individuals to purchase naloxone over-the-counter without a prescription. This legislation has drastically expanded access to naloxone, but has reduced the opportunity to train community members purchasing the medication. We plan to conduct a usability assessment of simulated naloxone in community members in the absence of training to assess the rate of successful administration and time to successful administration.

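### The Likert verdicts rest on one-way ANOVAs although route and instruction type are randomised together, and no follow-up test identifies which of three routes scored better

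*Combined protocol and SAP*

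**What the plan says.** - **Design** (Design section): each participant "will be randomly assigned a simulated naloxone kit containing either intramuscular standard, intramuscular simplified" or one of the other four route-by-instruction combinations. This is a 3 × 2 layout with one kit per person. Eligibility excludes people if they meet listed criteria "or they have previously participated in the trial", so nobody rates a second kit.
- **Outcomes** (Objectives, secondary): two separate Likert assessments are listed, "Likert-item assessment of the usability of the simulated naloxone product" and "Likert-item assessment of usability of the naloxone administration instructions".
- **Test** (Statistical Methods): Likert data are analysed by one-way ANOVA "with a significant difference defined as a p-value of less than 0.05 for comparison between administration methods and instruction methods". Data Analysis/Interpretation repeats the one-way ANOVA.
- **Decision rule** (Data Analysis/Interpretation): "a route or instruction type will be considered user preferred if the Likert-item data demonstrates a significantly better score on usability". It does not say which assessment decides, or how one route is to be set against another.
- **Neighbouring rule** (same section): a route is more user-friendly if it has a "statistically significantly higher rate of successful administration compared to another route of administration". The test planned for that is a Chi-square over the three groups, also without a pairwise step.

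**The concern.** There are two analytic gaps and two matters of wording.

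1. **Error term.** A one-way ANOVA by instruction type treats differences between routes as random error, and a one-way ANOVA by route does the same with instruction type. If routes are rated differently, the instruction comparison loses power that the design has already paid for.
2. **Which route.** A significant three-route ANOVA says only that the routes are not all rated alike. The rule then awards the label to a particular route. With no follow-up test specified, the analyst must choose one after seeing the data, and unadjusted pair tests would raise the false-claim rate.
3. **Wording.** The rule does not tie the route verdict to the product score and the instruction verdict to the instruction score. It also speaks of preference when each participant has used only one kit.

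At stake is whether the report's usability verdicts by route and instruction type are as sensitive as the design allows, and whether a named route has been shown to score better.

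**Working it through.** **Inputs from the documents.** Three routes, two instruction types, one kit per participant, and p < 0.05 per comparison. No sample size, item count, scale, SD or effect size is given, so there is no derived figure to reproduce.

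**Assumptions.** Six equal arms of 20 (60 per instruction type), one 5-point item per assessment, a 0.3 SD instruction effect, and one route rated d SD below the other two. Three response shapes were simulated: ceiling, symmetric, and a low-scoring minority.

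**Step 1: what the one-way test leaves in the error.** On an underlying continuous scale with within-arm variance 1, one route of three lower by d adds (1/3)(2/3)d² = 2d²/9 to the error variance.
- d = 0.3: 1 + 0.02 = 1.02
- d = 0.8: 1 + 0.142 = 1.142
- d = 1.5: 1 + 0.5 = 1.5

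With equal arms the instruction contrast itself is not made noisier, so the effective critical value becomes 1.96 × √variance: 1.98, 2.09 and 2.40. The true size falls to about 4.8%, 3.6% and 1.6%.

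**Step 2: approximate power on that scale.** The standardised effect is 0.3/√(2/60) = 1.643.
- Two-factor: P(Z > 1.96 − 1.643) ≈ 37.6%.
- One-way: about 36.8% (d = 0.3), 32.6% (d = 0.8) and 22.4% (d = 1.5).

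**Step 3: the same comparison on 5-point items (simulation).** Ranges run over the three shapes and repeated runs. Coarse scoring lowers all the figures, but the pattern is the same.

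| One route lower by | One-way, 20/arm | Two-factor, 20/arm | One-way, 50/arm | Two-factor, 50/arm |
|---|---|---|---|---|
| 0.3 SD | 26% to 34% | 27% to 35% | 53% to 69% | 54% to 69% |
| 0.8 SD | 22% to 30% | 26% to 34% | 51% to 64% | 55% to 69% |
| 1.5 SD | 14% to 21% | 25% to 34% | 38% to 53% | 54% to 68% |

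At 0.3 SD the gain is under one point. If participants are randomised singly to six arms, so that arm sizes vary, both tests hold their size (4.4% to 5.4%). The one-way test still loses power: 19% to 24% against 26% to 32% at N = 120 and 1.5 SD.

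For the route verdict the gain is small: a 0.3 SD instruction effect adds only 0.3²/4 = 0.0225 to the error variance.

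**Step 4: does a significant three-route test identify a route?** With two routes equal and one 0.5 SD worse (normal scores; 30, 70 or 150 per route), the overall test is significant in 50%, 87% and over 99% of runs. In 91% to 95% of those significant runs, the top route is not separated from the second.

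**Step 5: false route claims from pair tests, all routes alike.** Each pair is tested in the model fitted to those two routes.
- Without a gate: 11.7% to 12.7%.
- Only after a significant overall route test: 4.7% to 5.3%.

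With one route truly lower by 0.3, 0.8 or 1.5 SD, the gated false-claim rate between the two equal routes is 3.0% to 5.5%. With an error term pooled over all three routes it is 1.6% to 7.5%, because ratings that bunch at one end of the scale distort the pooled variance.

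**Step 6: both verdicts together.** With one score per verdict at 0.05 and independent scores, 1 − 0.95² = 9.75%.

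**The case against.** The strongest reply is that little is actually wrong.

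- **Validity.** Both factors are randomised, so the one-way comparison is unbiased, and its false-positive rate does not rise materially above 5%. This stands. The loss is power only, and only if routes are rated differently. Background reports that "intranasal administration with an atomizer or spray resulted in a higher administration success rate when compared to intramuscular injection", but that concerns success in trained users. It makes a rating difference plausible and gives no size for it.
- **Comparison named.** A reader might infer that the plan names no comparison at all. It does: Statistical Methods specifies comparison by administration method and by instruction method. With two instruction types no follow-up is needed. What is missing is the pairwise step among the three routes.
- **Deciding score.** A reader might infer that either score can decide either verdict. Under the same kind of assumptions that would give 8% to 10% false claims per verdict. But the two assessments are listed and collected separately, and the natural pairing (product with route, instructions with instruction type) already gives about 5%. Stating it is a small tightening. The survey form is not shown and the text at the study diagram breaks off, so item detail cannot be called missing.
- **Label.** A reader might infer that the protocol claims to measure choice between kits. The rule defines its own term, so this is a wording fault. No estimate or test changes.
- **The success rule.** A reader might take the user-friendly rule as a sound model, or as unaffected. It does name its measure and a comparator, but its three-group Chi-square has the same missing pairwise step.

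**Conclusion.** The concern holds as a minor point on the two secondary Likert objectives. The planned one-way ANOVA is valid but less sensitive than the factorial design allows, and on its own it cannot support a verdict that one particular route scored better.

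The power loss for the instruction verdict ranges from negligible (under one point when one route is 0.3 SD lower or less) to roughly 11 to 16 points (0.8 to 1.5 SD is where it becomes visible, and 1.5 SD gives the largest loss). The choice of pairwise procedure moves false route claims between about 12% and about 5% when routes are alike. All of these figures rest on an assumed scale, sample size and effect. The absence of a follow-up test does not.

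The documents do not support a finding of bias, of an inflated error rate in the ANOVA itself, or of any fault that is peculiar to the Likert rule and spares the success rule.

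**What to change.** 1. Take each Likert verdict from an ANOVA containing both randomised factors, route and instruction type. State in advance whether an interaction term is included and how the verdict reads if instruction effects differ by route.
2. Compare route pairs only after a significant overall route test, fitting the same model to the two routes concerned.
3. As wording, rest the route verdict on the product-usability score and the instruction verdict on the instruction-usability score. If an assessment has several items, fix before analysis whether their sum or one named item decides. Treat other Likert comparisons as descriptive.
4. Write 'rated more usable' in place of 'user preferred'.
5. Add a pairwise step to the success-rate rule as well, or say how its three-group test is to be read.

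**Cost.** No new data or visits are needed, and SPSS can fit the model. There is one added gating step, other Likert comparisons can no longer support a claim, and about 10% false claims remain across the two verdicts unless alpha is split. The changes must be made before the data are analysed.
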